## 3.METHODOLOGY:

### Patients and Methods:

- **Type of Study:** Prospective randomized clinical study.
- **Study Setting:** This study will be conducted in Ain Shams University Hospitals..
- **Study Period:** Expected for two years starting from 2019.
- **Study Population:**
  - Inclusion Criteria:*
    - ASA less than or equal II.
    - Age group: 21-65 years old.
    - The procedure expected to be completed within 2 hours.
  - Exclusion Criteria:*
    - Patients with expected difficult airway management.
    - Hemodynamically unstable patients.
    - Persistent cough or high airway secretions.
    - Severe Emphysema or clinical signs of active infectious disease.
    - Hypoxemia (PaO2 <60 mmHg) or hypercarbia (PCO2 >50 mmHg)
    - Coagulopathy (INR >1.5).
    - Obesity (BMI >30 Kg/m^2).
    - Infection at the injection site, allergy to local anesthetics.
    - Neurological disorders: seizures, intracranial mass or brain edema.
- **Sampling Method:** Randomized sampling by a computer generated random numbers table.
- **Sample Size:** 40 patients.

Sample size was calculated using PASS 11 program for sample size calculation and according to the (*Pompeo et al., 2004*) study, the mean PaO2 perioperatively in the awake group =  $-3 \pm 1.5$  mmHg and in the second group =  $-6.5 \pm 1.83$  mmHg. Sample size of 40 cases per group (total 40) can detect this difference with power 100% and  $\alpha$ -error 0.05.

- **Ethical Considerations:** Approval of the research ethical committee of faculty of medicine, Ain Shams University will be obtained and informed written consents will be taken from all the participants. The thoracic epidural placement will be performed by the most experienced person of the study team.

- **Study Tools:**

- **Anesthetic sheet.**

- **Visual analogue scale:** The Visual Analogue Scale (VAS) consists of a 10 cm straight line with the endpoints defining extreme limits of 'no pain at all' (0 cm) and 'pain as bad as it could be' (10 cm). The patient is asked to mark his pain level on the line between the two endpoints. The distance between 0 and the mark then defines the subject's pain score.

- **Anesthetic plan:**

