Patients in thoracic epidural anesthesia (TEA) group will pre-medicated using midazolam 3-4 mg intravenous (IV) and fentanyl 50 mcg IV. Then patients will placed in the setting position. Under aseptic precautions, skin infiltration with local anesthesia will be done using a 5ml syringe containing 5ml of 1% lidocaine. An epidural catheter will be inserted between T3—T4 and T4—T5 for thoracic procedures meeting the inclusion criteria. A test dose (5 ml) of 2% lidocaine will be given, followed by 15-20 ml of bupivacain 0.5% and 50 mcg of fentanyl. The objective is to achieve sensory and motor block between C7 and T7 levels. At this level diaphragmatic respiration is maintained. In case of persistent hemodynamic instability or persistent hypoxemia, the patients will be transferred to the other group.

Patients will receive general anesthesia (GA) as follows, after proper assessment of the airway and anticipation of difficult airway, all patients will receive premedication in the form of 3-4 mg midazolam IV, ranitidine 50 mg IV as H2 receptor antagonist, metoclopramide 10 mg IV and dexamethasone 4 mg IV as post-operative nausea and vomiting (PONV) prophylaxis. Start preoxygenation with 100% O2 on 8 L/min for 3 min via face mask. Induction of anesthesia with propofol (2mg/kg) and fentanyl (1 mcg/kg). Tracheal intubation and double endotracheal tube insertion will be facilitated with cisatracurium 0.1 mg/kg. and confirmation of it is position will made by fiberoptic bronchoscopy, Anesthesia will be maintained with isoflurane (1-2 %) and cisatracurium (0.05 mg/kg per dose). After the end of the operation, anesthesia will be discontinued, and extubation of the patient will be done after full neuromuscular recovery after reversal of muscle relaxant by neostigmine (0.05 mg/kg) and atropine (0.02 mg/kg).

Postoperative pain and opioid consumption will be assessed after regaining of sensation using the VAS. Post-operative analgesia will be offered in regular doses of Paracetamol 1gm IV every 6 hours for the following 48 hours. Rescue analgesia will be given when VAS  $\geq$ 3, in the form of an injection of Pethidine 50 mg diluted in 10ml normal saline 0.9%, to be given intravenously slowly over 10 min.

- **Measured outcomes**

- **Primary outcome:**

Perioperative changes in blood gases [ Time Frame: Immediately before operation, intraoperatively per hour, and postoperatively per 2 hrs till 24h ]

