Ratio of arterial oxygen tension to fraction of inspired oxygen (PaO2/FiO2), arterial carbon dioxide tension (PaCO2). Hypoxemia is defined as peripheral oxygen saturation (SpO2) < 92% on room air with a need for oxygen supplementation.

- **Secondary outcomes:**

- Postoperative pain using the Visual Analogue Scale (VAS), [ Time Frame: Postoperatively at 3h,12h and 24h ].
- Postoperative opioid (Pethidine) consumption [ Time Frame: Postoperatively during the 24h after regaining of sensation ].
- Hospital stay [ Time Frame: from day of operation to discharge; average, 5 days ]
- Perioperative changes in cardiocirculatory variables including heart rate (HR) and mean arteial pressure (MAP) [ Time Frame: Immediately before the operation, intraoperatively per hour, and postoperatively per 2 hrs till 24h ]
  - Bradycardia is defined as:  $HR \leq 50$  bpm
  - Hypotension is defined as a decrease in systolic blood pressure  $>20\%$  of basal.
  - Hypertension is defined as an increase insystolic blood pressure  $>20\%$  of basal.
- The onset of ambulence. Rate of occurence of falling after ambulence will be recorded in each group. [Time Frame: During the 24 hours after regaining of full motor power].
- Number of episodes of PONV [Time Frame: During the 24 hours postoperatively].
- **Statistical Analysis:** The collected data will be revised, coded and introduced to a PC using statistical package for social science (SPSS 15.0.1. for windows; SPSS Inc, Chicago, IL, 2001).
 

Data will be presented as mean and standard deviation (+- SD) for quantitative parametric data, median and range for quantitative non-parametric data and as numbers and percentage for qualitative data. Suitable analysis will be done according to the type of data obtained.  $P < 0.05$  will be considered significant.

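### The 24 h pethidine count starts at an undefined return of sensation that the epidural can delay, so the arms may be compared over different postoperative hours

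*Combined protocol and SAP*

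**What the plan says.** In section 3 (Methodology) of the combined protocol and SAP, the secondary outcomes give the pethidine time frame as "Postoperatively during the 24h after regaining of sensation". The postoperative analgesia paragraph uses the same starting event for both arms: "Postoperative pain and opioid consumption will be assessed after regaining of sensation using the VAS". Neither place gives a test, a dermatome, an assessor or a clock time for it.

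For Group A, the epidural paragraph states: "The objective is to achieve sensory and motor block between C7 and T7 levels". For Group B, no regional block is described. The only recovery milestone given is extubation once neuromuscular function has fully recovered, and it is not linked to sensation.

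Several other outcomes run on plain postoperative time in both arms. Blood gases are taken "Immediately before operation, intraoperatively per hour, and postoperatively per 2 hrs till 24h", heart rate and mean arterial pressure "Immediately before the operation, intraoperatively per hour, and postoperatively per 2 hrs till 24h", and nausea and vomiting episodes are counted over the 24 hours after surgery. The Statistical Analysis paragraph has no rule for aligning observation windows.

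**The concern.** A randomised comparison of drug use needs both arms to be observed over the same period, with a start that treatment cannot move. Here the start depends on the assigned anaesthetic. A sensory block is the intended effect of the epidural, so Group A's clock can start later than Group B's. Group A's early postoperative hours then drop out of its total, and hours beyond 24 are added.

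The missing definition adds to this. If sensation in Group B is taken as emergence from anaesthesia, that clock starts close to the end of surgery; if it is taken as something else, it starts elsewhere. The documents leave the choice open.

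At stake is the reading of one recovery-related secondary outcome. The stated aim is to speed up recovery, and opioid use is an outcome on which a block would be expected to act. A difference in pethidine, or the lack of one, could come partly from the window.

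**Working it through.** There is no planned figure to reproduce: the documents state no expected pethidine use, standard deviation or power for this outcome.

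**Inputs from the documents.** Window length 24 h; rescue pethidine in 50 mg injections when VAS is 3 or more; "The procedure expected to be completed within 2 hours"; no postoperative epidural infusion described. The last two mean that the residual block, and hence s, could be short.

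**Overlap.** If sensation returns s hours later in A than in B, the shared postoperative time is 24 - s: 23 h at s = 1, 22 h at s = 2, 20 h at s = 4, 18 h at s = 6.

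**Direction.** Let A(a,b) be Group A's pethidine between postoperative hours a and b. Suppose Group B's clock starts at end of surgery, so that B's total is the same on both clocks and s is A's delay from end of surgery. Then:

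- written clock: A(s, s+24)
- common clock: A(0, 24)
- written minus common = A(24, 24+s) - A(0, s)

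If A uses nothing while blocked, A(0, s) = 0 and the difference is A(24, 24+s), which cannot be negative. The written clock then cannot overstate a saving and may understate it, whatever the trend in demand. If A(0, s) is larger than A(24, 24+s), the sign reverses: one 50 mg dose before sensation returns and none after hour 24 gives 0 - 50 = -50 mg. If Group B's clock starts b hours after surgery, B's total also changes, by B(24, 24+b) - B(0, b), and the sign is not fixed.

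**Illustration of size (all assumed).** Demand is proportional to 2^(-t/h), Group B is counted over 0 to 24 h, and Group A uses none before s and then follows the same curve. The A/B ratios are:

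- written: 2^(-s/h)
- common: (2^(-s/h) - 2^(-24/h)) / (1 - 2^(-24/h))
- constant demand: written 1.000, common (24 - s)/24

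Each cell shows written vs common, with the gap in percentage points:

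| s | h = 8 h | h = 12 h | h = 24 h | constant |
|---|---|---|---|---|
| 1 h | 0.917 vs 0.905 (1.2) | 0.944 vs 0.925 (1.9) | 0.972 vs 0.943 (2.8) | 1.000 vs 0.958 (4.2) |
| 2 h | 0.841 vs 0.818 (2.3) | 0.891 vs 0.855 (3.6) | 0.944 vs 0.888 (5.6) | 1.000 vs 0.917 (8.3) |
| 4 h | 0.707 vs 0.665 (4.2) | 0.794 vs 0.725 (6.9) | 0.891 vs 0.782 (10.9) | 1.000 vs 0.833 (16.7) |
| 6 h | 0.595 vs 0.537 (5.8) | 0.707 vs 0.609 (9.8) | 0.841 vs 0.682 (15.9) | 1.000 vs 0.750 (25.0) |

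With an assumed Group B mean of 100 to 200 mg, the gap is 1.2 to 8.3 mg at s = 1 h and 5.8 to 50.0 mg at s = 6 h.

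**Opposite case.** If Group A used pethidine at Group B's rate throughout, including before sensation returned, the common ratio would be 1.00. With h = 12 h the written ratio would be 0.891 at s = 2 h and 0.707 at s = 6 h: an apparent saving produced by the window alone.

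**The case against.** The strongest reply is that this is a choice of estimand. Both arms get the same rule and a window of the same length, and need for pethidine once pain can be felt is a coherent quantity. The choice may be deliberate. That stands as a reason to keep the measure. It does not make it suitable as the only measure, because it removes the block's early benefit from a trial that asks about recovery, and the plan gives no reason for departing from the postoperative clock used for blood gases, haemodynamics and nausea and vomiting.

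A second reply is that the gap is one of definition: the event is not specified for Group A either, and emergence is the obvious reading for Group B. The first part is correct. But even with emergence written in, Group A's clock can still start later, so a definition alone does not align the windows.

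A third reply is that the effect may be small. That also stands. With surgery expected within 2 h and no infusion described, the delay may be short. On the assumptions above, a 1 h delay is worth at most about 8 mg against a 50 mg dose, and the 50 mg gap needs a 6 h delay, constant demand and a 200 mg mean together.

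A reader might infer that the written clock is bound to hide an opioid saving, or hides some stated fraction of it. The documents do not support that. They give no block duration, no demand profile and no start time for Group B, and the rescue sentence carries no explicit condition that sensation has returned, so uncounted early doses in Group A cannot be excluded.

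**Conclusion.** The point holds as a weakness in how one secondary outcome is defined. As written, the pethidine total starts at a post-randomisation event that one arm's treatment can delay, that is not operationally defined in either arm, and that has no stated meaning after general anaesthesia. The arms can therefore be compared over windows sharing only 24 - s postoperative hours.

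The value of s is not in the documents, so the size cannot be stated; the figures above only show how it would vary. The direction is conditional: no overstatement of a saving if Group B's clock starts at end of surgery and Group A uses nothing while blocked, and possibly the reverse if Group A receives pethidine before sensation returns. The primary blood gas outcome is not affected, and nothing here bears on the sample size. It is a cheap improvement.

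**What to change.** Define pethidine consumption as total mg from 0 to 24 h after end of surgery in both arms. Record the times of end of surgery and of return of sensation for every patient. Keep the total over the 24 h after return of sensation as a supplementary measure, and state for each arm what that event is and how it is judged.

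The cost is one reworded outcome line, a short definition per arm and two recorded times per patient, with no extra patients or visits. The supplementary total needs dose recording to continue to 24 h after sensation returns, as the present wording already requires. The downside is that the common-clock total includes any residual block, so it does not isolate need once pain can be felt; the supplementary measure covers that. No dose or rescue rule changes.

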**December 2019**

**What is already known on this subject? And  
What does this study add?**

Video-assisted thoracic surgery (VATS) is usually performed with general anesthesia and single lung ventilation. However, performing thoracic surgery under awake regional anesthesia has several potential advantages including avoidance of airway trauma and ventilator dependence associated with endotracheal intubation, besides promoting enhanced recovery after surgery and shorter mean hospital stay.

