## 2.AIM/ OBJECTIVES:

The aim of this study is to investigate the feasibility and the effect of Thoracic Epidural Anaesthesia for awake thoracic surgery to speed up recovery in patients as well as avoiding the complications accompanying General Anesthesia with one lung ventilation.

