In the anesthesia clinic, an informed written consent will be taken from every patient one day before the surgery. The VAS will be explained to the patients. Anesthesia will be provided according to the hospital protocol in respect to preoperative investigations, fasting hours and intra-operative monitoring and drugs.

- **Study Interventions:** The study will include 60 patients fulfilling the inclusion criteria. They will be randomized into 2 equal groups by a computer generated random numbers table, each consisting of 30 patients, namely group A and group B.

- **Group A:** Awake Patients will receive sole Thoracic Epidural Anesthesia.

- **Group B:** Patients will receive General Anesthesia with one lung ventilation.

Preoperatively, Intravenous access will be established and lactated ringer solution will be infused. Monitors for non-invasive blood pressure, heart rate, electrocardiogram (ECG), pulse oximetry (SpO2), and capnography for end tidal CO2 (ETCO2). Invasive arterial line is inserted for serial perioperative ABGs

Patients will be observed for any complications either related to the procedure e.g: hematomas or related to drugs injected e.g: hypotension, bradycardia, hypoxemia, nausea, vomiting or any other adverse effects and will be managed.

- In case of hypotension (drop of blood pressure >20% of baseline reading), 10-30mg of ephedrine diluted over 10ml normal saline 0.9% will be given intravenously by titration according to the blood pressure.
- In case of bradycardia, when it is associated with hypotension or any signs of impaired perfusion, 0.5mg of atropine will be given and can be repeated every 3-5min with a maximum of 3mg.
- In case of fall in peripheral SpO2, supplemental oxygen will be given to keep SpO2 above 94%.

- In case of postoperative nausea and vomiting (PONV), ondansetron 4mg diluted in 10ml normal saline 0.9% will be given intravenously slowly over 10 min.

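### Hospital stay is counted to actual discharge, with no common discharge criteria and no masking described, so the comparison between arms is open to expectation bias

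*Combined protocol and SAP*

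**What the plan says.** Under Secondary outcomes in section 3 (Methodology), the protocol defines "Hospital stay [ Time Frame: from day of operation to discharge; average, 5 days". This is one of several secondary outcomes, and they are not ranked. The primary outcome is perioperative blood gases.

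The design is described only as "Prospective randomized clinical study". Neither that line nor any other part of the document mentions masking of patients, ward staff or assessors. The two arms under Study Interventions are:

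- Group A: "Awake Patients will receive sole Thoracic Epidural Anesthesia".
- Group B: "Patients will receive General Anesthesia with one lung ventilation".

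The expected direction is on record. The opening summary includes, among the potential advantages of the awake technique, "promoting enhanced recovery after surgery and shorter mean hospital stay". Section 2 (Aim/Objectives) says the technique is studied "to speed up recovery in patients as well as avoiding the complications accompanying General Anesthesia with one lung ventilation".

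The document gives no discharge criteria and no definition of readiness for discharge, and it does not say who decides.

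**The concern.** Actual discharge is a human decision. It depends on the patient's condition, but also on the judgement and habits of the people who sign it off. Randomization balances the patients at allocation. It does not protect a judgement made days later by someone who may know which technique was used and which result is hoped for.

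Four features occur together here: the endpoint is discretionary, no written standard is shared by the arms, no masking is described, and the protocol states which arm should do better. If awake patients are released somewhat sooner because they are expected to be ready sooner, the trial will report a shorter stay that reflects earlier permission to leave rather than faster recovery. Faster recovery is part of the stated aim, so a reader is likely to give such a result weight even though it is a secondary outcome.

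**Working it through.** **1. The plan's own figure.** The only power statement concerns the change in PaO2: -3 (SD 1.5) versus -6.5 (SD 1.83) mmHg, α 0.05, power 100%.

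- Difference: 6.5 - 3 = 3.5 mmHg.
- Pooled SD: √((1.5² + 1.83²)/2) = √2.799 = 1.673 mmHg.
- At 20 per group, the smallest reading of the stated sample size: 3.5 / (1.673 × √(2/20)) = 6.61, and power = Φ(6.61 - 1.96) = 0.999998.

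The stated 100% therefore reproduces, and it does so at 30 and 40 per group as well. It says nothing about hospital stay, for which the document gives no calculation and no SD.

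**2. Inputs for an illustration on hospital stay.**

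- Group size: 30 per group, from Study Interventions. The Sample Size entry gives both 40 per group and a total of 40 (20 per group), so 20 and 40 are shown too. These figures need reconciling in their own right.
- α: 0.05, taken as two-sided because the document does not say.
- SD of stay: not in the document. Assumed range 1 to 3 days.
- Shift in discharge due to expectation: not in the document. Assumed 0.5 day, with 0.25 day as a milder case.
- True effect: zero.

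**3. Formula.** Let k = shift / (SD × √(2/n)). The two-sided false-positive rate is P(Z > 1.96 - k) + P(Z < -1.96 - k).

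**4. One case in full.** Shift 0.5 day, SD 2, n = 30: k = 0.5 / (2 × √(2/30)) = 0.5 / 0.516 = 0.968. The rate is P(Z > 0.992) + P(Z < -2.928) = 0.161 + 0.002 = 0.162.

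**5. The range for a 0.5-day shift.**

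| Assumed SD (days) | 20 per group | 30 per group | 40 per group |
|---|---|---|---|
| 1 | 35% | 49% | 61% |
| 1.5 | 18% | 25% | 32% |
| 2 | 12% | 16% | 20% |
| 3 | 8% | 10% | 12% |

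The nominal rate is 5%. With a 0.25-day shift and an SD of 2, the rate is 7.7% at 30 per group and 6.8% at 20 per group. A larger trial makes this worse, because a fixed bias is then detected more reliably.

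**6. Whether the analgesia course sets a lower limit on stay.** The protocol says "Post-operative analgesia will be offered in regular doses of Paracetamol 1gm IV every 6 hours for the following 48 hours". Suppose, contrary to anything written, that nobody could leave before 2 days. Take a lognormal time to readiness with sigma 0.5, so that the mean is the median × exp(0.125) = median × 1.133.

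| Medians (days) | Means (days) | Difference in means, no limit | Difference in means, 2-day limit |
|---|---|---|---|
| 4 vs 5 | 4.5 vs 5.7 | 1.13 | 1.11 |
| 2 vs 3 | 2.3 vs 3.4 | 1.13 | 0.93 |
| 1.5 vs 2.5 | 1.7 vs 2.8 | 1.13 | 0.77 |

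Only the first row is near the protocol's stated average of 5 days, and there the effect is negligible.

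**The case against.** **Length of stay is a legitimate pragmatic endpoint.** It is simple, it matters to patients and hospitals, and counting to discharge is common practice. This stands, and it is why actual stay should still be reported. It does not answer the lack of a common standard in a trial with no masking described.

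**Nobody has shown that the discharging staff know the arm.** This stands in part. The operating team must know. The document does not say who decides discharge or what the ward is told. Knowledge on the ward is a reasonable inference, since nothing is planned to prevent it, but it is not a documented fact.

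**The numbers come from assumptions.** This stands. Both the shift and the SD are assumed, and at 30 per group the result runs from 10% to 49% for the same half-day. The table illustrates the mechanism and does not estimate the bias in this trial.

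**A checklist filled in by unmasked staff is not masked.** This stands too. Written criteria narrow discretion without removing it.

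A reader might also infer two stronger points that the document does not support:

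- *The 48-hour intravenous paracetamol builds a floor into hospital stay.* The course is offered, and the document nowhere makes its completion a condition of discharge. Even as a hard limit at 2 days, it would hardly matter near the stated 5-day average.
- *Hospital stay is the main measure of recovery speed.* The secondary outcomes are unranked, and another of them also measures recovery: "The onset of ambulence. Rate of occurence of falling after ambulence will be recorded in each group".

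**Conclusion.** The point holds as a weakness of one unranked secondary outcome. Hospital stay is counted to actual discharge, without common criteria and without any described masking, in a comparison where the technique is plain to the treating team and the hoped-for direction is written down. Expectation bias in favour of the awake arm is a realistic possibility that the plan does nothing to limit.

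Its size is unknown. If knowledge of the arm moved discharge by half a day and there were no true effect, the false-positive rate at 30 per group would lie between about 10% (SD 3 days) and 49% (SD 1 day). At 20 per group with an SD of 2 days it would be 12%. The SD, the half-day shift and the two-sided test are all assumptions. The primary outcome is not affected by this point. No conclusion is drawn about a floor from the analgesia course.

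**What to change.** Before enrolment:

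1. Write down the department's own discharge-readiness criteria in the protocol and apply them identically in both arms at each scheduled ward round.
2. Record the round at which all criteria are first met. Analyse time from end of surgery to readiness next to actual length of stay, and state that its resolution is limited to the interval between rounds.
3. Where existing staffing allows, have readiness recorded by someone not told the arm. State in the protocol who decides discharge and whether that person will know the arm.
4. State how the 48-hour analgesia course relates to discharge, so that readers need not guess.

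The cost is slightly more recording on the ward sheet at each round until readiness, plus the work of writing the criteria down if the department has none in writing. No change to treatment or sample size is needed. Bias is reduced rather than eliminated, particularly if the recorder knows the arm, and the report should say so.
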